4.1 Primary and secondary endpoint

Primary endpoint: the geometric mean based ERR of *T. trichiura* egg counts assessed by Kato-Katz microscopy pre-treatment and 14-21 days post-treatment.

Secondary endpoint: CR of *T. trichiura* as well as CRs and ERRs for *A. lumbricoides* and hookworm assessed by Kato-Katz at 14-21 days post-treatment. In addition, tolerability of treatment (AEs), infection status and intensity assessed at baseline and 14-21 days post-treatment by novel diagnostic tools (FECPAK-G2 and/or PCR), infection status and intensity derived by Kato-Katz at 5-6 weeks and 3 months post-treatment and PK/PD parameters of the study drugs will be assessed.

4.2 Type of trial

Randomized controlled trial, open-label with masked outcome assessor.

4.3 Trial design

4.3.1 Baseline survey and screening

A randomized-controlled trial will be conducted with five treatment arms to be followed-up over a 3-month period. This trial will be conducted as a school-based study on Pemba Island (Zanzibar, Tanzania). Several secondary schools in areas with suspected high *T. trichiura* endemicity as identified from previous research and experience of our local collaborators will be visited. In each selected school, adolescents aged 12-19 years will be invited for study participation. The Zanzibar education system has adopted a 12-year compulsory basic education cycle with abolished school fees and parents' contributions since 2015 leading to high general enrolment rates for secondary schools (85% of eligible children finalize the last primary grade level) but also comparably high ordinary secondary level survival of more than half of all pupils (54%) [22]. Entering school over-age is a common occurrence in Zanzibar, thus ages of secondary level pupils may well range from 12 to 19 years of age. We are thus confident that recruitment of adolescents aged 12-19 years through a school-based approach is not only more efficient than working in communities but also still representative for the total population of this age strata. Adolescents are within the main target group of helminth control programs and are listed among potential receivers of moxidectin that is, so far, only approved from 12 years of age onwards [23].

The study includes one baseline and three follow-up assessments at 14 – 21 days, 5-6 weeks and 3 months. The study is designed as a five-arm trial including two arms with combined treatment through co-administration of separate tablets (arm A; moxidectin/ albendazole, arm B; ivermectin/ albendazole) and three arms with single drug administration (arm C; albendazole, arm D; ivermectin, arm E; moxidectin).

[figure not shown]

Figure 1: Design and timeline of the randomized-controlled trial to be implemented on Pemba Island (Tanzania).

4.3.2 Diagnosis

At baseline, all participants will be asked to provide two stool samples (within a maximum of 7 days). From each stool specimen, duplicate Kato-Katz thick smears (41.7 mg each) [24] will be prepared and read under a microscope for eggs of *T. trichiura*, *A. lumbricoides* and hookworm by experienced technicians. To ensure quality of hookworm diagnosis, 10% of the samples will be divided into two subsamples; one of the containers will keep its original participant ID, whereas the second container will be labeled with a new ID (assigned by the co-PI). Duplicate Kato-Katz will be prepared from both containers and the findings compared. For hookworm, results are considered correct if no difference in presence/absence is found. For quality control of *A. lumbricoides* and *T. trichiura* egg counts, 10% of slides will be re-read by another laboratory technician. Results are considered correct if the following tolerance margin is not exceeded: (i) No difference in presence/absence of *A. lumbricoides* and *T. trichiura* (ii) egg counts are +/-10 eggs for counts \leq 100 eggs or +/-20% for counts $>$ 100 eggs (for each species separately). In case discrepancies above the tolerance margin are noted in one or more slides, the respective slides are re-read by the local technicians. The new results are discussed, so that in case of discordant results, slides can be re-evaluated to reach consensus. The same slides might further be re-read by an automatized reading system (Kato-Katz 2.0) if available at study start.

All microscopically analyzed quadruplicate Kato-Katz thick smears will be destroyed after passing the quality control. Additionally, a portion of 1.5-2 g of stool from each specimen will be preserved in 70% ethanol and shipped to a reference laboratory for polymerase chain reaction (PCR) analysis (to be determined) [25]. The same sampling procedure and diagnostic approach will be applied at days 14-21, 5-6 weeks and 3 months post-treatment. At baseline and 14-21 days post-treatment, 3g of the remaining stool specimen will be used for analysis with a further developed version of the FECPAK-G2 device using a similar laboratory protocol as applied in previous studies [26, 27].

4.3.3 Clinical examination

A clinical examination of the study participants assessing general health, anthropometric parameters including height and weight as well as tympanic temperature using an ear thermometer will precede the treatment. Each participant will be asked to provide a finger-prick blood sample for hemoglobin (Hb) levels, which will be detected using a HemoCue analyzer (Hb 301 system, Angelholm, Sweden). To avoid accidental treatment of pregnant girls/women all female participants will be asked to provide a urine sample to be subjected to a pregnancy RDT at baseline and at the end of the study 3 months after treatment. Girls/women will be individually counselled that they should not become pregnant during the entire study period. All trial participants will further be asked about existing clinical symptoms before drug administration.

4.3.4 Adverse events assessment

Participants will be kept for 3 hours after treatment administration to observe any possible acute AEs and reassessment will be done at 24h post-treatment. Additionally, interviews will be conducted to determine the emergence of clinical symptoms such as headache, abdominal pain, itching, nausea, vomiting and diarrhea directly before treatment within the scope of baseline assessment. At 3 and 24 hours after treatment and retrospectively at days 14 – 21 as well as 5-6 weeks and 3 months post-treatment, participants will again be interviewed for the assessment of adverse events (AEs). Symptoms arising within the timespan of 24 hours after treatment and the respective follow-up time points will be monitored passively by teachers or local health workers who will report incidences to the study team. Any symptoms are recorded in the CRF and immediate action will be undertaken according to the judgement of a study physician if indicated.

4.3.5 Assessment of efficacy after treatment

The efficacy of the treatment will be determined 14-21 days post-treatment by collecting another two stool samples, which will be microscopically examined for *T. trichiura* using duplicate Kato-Katz thick smears. Participants will be considered cured if no *T. trichiura* eggs are found in the follow-up stool samples. Eggs per gram will be assessed by adding up the egg counts from the quadruplicate Kato-Katz thick smears and multiplying this number by a factor of six. Geometric and arithmetic mean egg counts

will be calculated for the different treatment arms before and after treatment to assess the corresponding ERRs. At the end of the study all participants remaining positive for any STH infection will be treated with the currently best recommended treatment, i. e. ivermectin/ albendazole against *T. trichiura* and hookworm and albendazole against *A. lumbricoides*.

4.3.6 Pharmacokinetic studies

The exposure-response correlation study will be performed in a maximum of 15 participants in the combination chemotherapy treatment arms and 10 participants in the monotherapy treatment arms, amounting to a subsample of 60 participants overall. This number of participants was determined to be representative of the study community taking into account the relatively low variability among PK values within a population. The absorption of all study drugs is known to be better after consumption of a high-fat meal, therefore study participants will receive a local high-fat breakfast before treatment [16]. Since PK population parameters of all study drugs are available [31], a sparse sampling approach can be applied to describe the PK profiles of the individual drugs upon co-administration as well as a potential interference between moxidectin or ivermectin and albendazole. Within a sparse sampling approach, instead of describing the PK profile for each participant separately, samples are allocated to different time points and individuals within the same treatment. Statistical inferences are performed to characterize the population-based PK profile of a specific treatment arm. This approach allows for a reduced number of samplings per participant and renders a PK characterization well tolerable. To this end, a small drop of blood from the fingertip will be taken. The sampling will be performed according to the following scheme:

- A maximum of 4 finger pricks will be done per participant throughout the whole PK study
- Of these 4 finger pricks per participant, a maximum of 3 pricks will be done on the same day
- The intervals between the pricks done on the same day will be at least 1h
- The whole PK study will be completed between day 0 and day 7

The sparse sampling scheme will allow for a sufficient number of data points at a subsample of 60 participants to model the PK profiles of the drugs. The exact time points will have to be adapted according to PK data gathered during a current trial conducted by our group for the evaluation of the efficacy of moxidectin against *Strongyloides stercoralis*. Capillary blood ($\leq 30\mu\text{L}$, i.e. $10\mu\text{L}$ for ivermectin and albendazole and $30\mu\text{L}$ for moxidectin) will be collected by puncture with a finger prick. Two microsamples (duplicates) will be taken with one finger prick. Each time, the drop of blood (10 – $30\mu\text{L}$) will be directly transferred on filter paper or Mitra® sticks which should dry for approximately one hour. The dried sticks and filter paper will be transported to Swiss TPH, Basel, and stored at -20°C until analysis. The quantification of the study drugs will be performed using the validated liquid chromatography tandem mass spectrometry (LC-MS/MS) method as described elsewhere [20, 31]. Drug concentrations will be calculated by interpolation from a calibration curve with a lower limit of quantification of 1-5ng/ml. 7% of the sample duplicates will be analyzed for quality control, and the

measured concentrations will be used to determine between-run and overall precision and accuracy of the analysis.

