Measurements & procedures	
Two stool samples will be collected if possible on two consecutive days or otherwise within a maximum of 7 days. The medical history of the participants will be assessed with a standardized questionnaire, in addition to a clinical examination carried out by the study physician before treatment.
 
All participants will be interviewed before treatment and after 3 and 24 hours (active surveillance) and retrospectively again at 14 - 21 days as well as 5-6 weeks and 3 months after treatment about the occurrence of adverse events (AEs). Any potential AEs happening between 24 hours and the respective follow-up time points will be monitored passively and medical intervention as determined suitable by a study physician provided if necessary.

	
The efficacy of the treatment and potential extended effects on follow-up prevalence will be determined around 14 - 21 days, 5-6 weeks and 3 months post-treatment by collecting another two stool samples.
 
All stool samples will be examined with duplicate Kato-Katz thick smears for T. trichiura, A. lumbricoides, and hookworm. From the remaining stool specimen, 3g will be analyzed with the FECPAK-G2 platform and 1.5-2g will be preserved in 70% ethanol and shipped to Swiss TPH, Basel or another reference laboratory for subsequent PCR-analysis.
 
Each participant will be asked to provide a finger-prick blood sample for hemoglobin measurement at baseline. At the same time, anthropometric measurements (i.e. height, and weight) will be taken for all participants. To determine PK/PD parameters of the study drugs, a subsample of 60 willing study participants of all treatment arms will be asked to provide a maximum of 4 micro blood samples using finger pricks at defined time points between day 0 and day 7.

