In this trial, we test for non-inferiority of both currently approved and available drug combinations (i.e. moxidectin/ albendazole against ivermectin/ albendazole) and for superiority of the combination therapy compared to the respective monotherapies. Furthermore, potential extended effects through a prolonged efficacy assessment scheme in adolescents in Pemba (Tanzania) are examined. Follow-up will be conducted at approx. 14-21 days, 5-6 weeks and 3 months post-treatment to assess co-benefits on worm burden reduction from the relatively long half-life of moxidectin ($T_{1/2}$: 491-832 hours) [11, 12] compared to ivermectin ($T_{1/2}$: 16-32 hours; increasing with age) [13]. Given the comparatively long half-life of moxidectin, the standard follow-up period of 14-21 days recommended by WHO might not be sufficient to reveal the full potential of the drug. Therefore, two more follow-up time points will give the opportunity to investigate potential extended effects on infection status and intensity. Results from this trial will inform decisions on how anthelminthic combination therapy could be introduced into existing MDA programs and, therefore, provide a valuable adjunct tool for interrupting STH transmission.

The pharmacokinetic/-dynamic (PK/PD) characterization of a drug is essential to understand the response of the human body to a drug and vice versa, especially in populations that physiologically differ from healthy adults. Physiological characteristic like mal- or undernutrition or intestinal worms, such as *T. trichiura*, can potentially affect the PK of a drug.[14, 15]. For moxidectin, clinical pharmacokinetics have so far exclusively been assessed in a limited number of healthy adults [16, 17]. A trial currently being conducted by our group will characterize PK and evaluate PK/PD parameters of moxidectin in adults infected with *Strongyloides stercoralis*. Our study will be the first one to provide information on the PK, PK/PD on all three drugs in this population and thus guide optimal drug dosing in *T. trichuris*-infected adolescence in Pemba. Additionally, we aim to provide novel information on the possible interplay of moxidectin and ivermectin with albendazole when co-administered. For this it is necessary to take not only samples in the combination arm but also in the monotherapy arms.

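### Pharmacokinetic sampling stops at day 7, about 0.20–0.34 of moxidectin's stated half-life, so two of the five listed interaction parameters (t½ and AUC(0–inf)) cannot be compared reliably between the moxidectin arms

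*Combined protocol and SAP*

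**What the plan says.** - **Window.** Section 4.3.6: "The whole PK study will be completed between day 0 and day 7". The synopsis agrees: selected participants "provide a maximum of 4 micro blood samples using finger pricks at defined time points between day 0 and day 7". Table 1 in section 4.6 shows no pharmacokinetic sampling after day 7. Each participant has at most four finger pricks, at most three of them on one day.
- **Numbers.** Up to 15 participants in each combination arm and 10 in each monotherapy arm. For moxidectin the comparison is arm A (15) against arm E (10).
- **Half-lives.** Section 2 refers to the "relatively long half-life of moxidectin ($T_{1/2}$: 491-832 hours" and gives 16–32 h for ivermectin.
- **Interaction parameters.** Section 8.3 has one list for all study drugs: Cmax, tmax, AUC(0–24h), AUC(0–inf) and t½. The interaction is to be judged on these. The synopsis endpoints include moxidectin with albendazole.
- **Model.** Section 8.3 names nonlinear mixed-effects modelling in Monolix and a precision target of SE < 25%. It does not say whether co-administration may act on bioavailability, on clearance or on any parameter.
- **Earlier knowledge.** Section 4.3.6: "Since PK population parameters of all study drugs are available [31", where reference 31 is, by its title, about albendazole and its metabolites. Section 2: "For moxidectin, clinical pharmacokinetics have so far exclusively been assessed in a limited number of healthy adults". Sections 2, 4.3.6 and 8.3 also point to other pharmacokinetic trials of the group.
- **Variability.** Section 4.3.6 relies on "relatively low variability among PK values within a population" and section 8.2 calls it moderate. Neither gives a CV.

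**The concern.** A half-life is estimated from decline. Over 168 h moxidectin hardly declines, so its terminal slope is poorly determined, and so is any AUC extrapolated to infinity with that slope. The window is ample for ivermectin, so the difficulty belongs to one drug.

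At stake is how the moxidectin–albendazole result is read. If arms A and E showed no difference in t½ or AUC(0–inf), a reader could not tell whether that reflects the drugs, the short window or the model. The unnamed interaction model matters because it alone can turn the same AUC(0–inf) contrast from precise to nearly uninformative. If it were chosen after the data are seen, either impression could result.

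**Working it through.** **Plan's own figure.** The subsample is 2 × 15 + 3 × 10 = 60, as stated. The documents give no precision calculation for the interaction.

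**Step 1: window against half-life** (inputs from sections 2 and 4.3.6).
- Moxidectin: 168/491 = 0.342; 168/832 = 0.202.
- Ivermectin: 168/32 = 5.25; 168/16 = 10.5.

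**Step 2: share of AUC(0–inf) beyond day 7.** With mono-exponential decline the share is 2^(−168/t½): 0.789 (491 h) and 0.869 (832 h). The concentration therefore falls by only 21% and 13% over the window. For ivermectin at 32 h the share is 0.026. If the terminal phase carries only a fraction w of the AUC, the share is w × 2^(−168/t½): 55–61% at w = 0.7 and 39–43% at w = 0.5. The documents do not give w. An early distribution phase lowers the share but makes the terminal slope harder to identify.

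**Step 3: precision.** These inputs are assumptions: one compartment, absorption half-life 1.2 h, between-subject CV 30%, residual CV 15% or 30%, and no prior on clearance. Each participant contributes F = J′(JΩJ′ + σ²I)⁻¹J on the log scale for ka, V and CL, with Ω = ln(1 + 0.30²) on the diagonal and σ² = ln(1 + CV²). M is the average F over a D-optimal mix of four-sample schedules (1–12 h, then daily to 168 h, at most three per day). Per-arm variances come from M⁻¹/n. The between-arm variance uses 1/10 + 1/15 = 1/6.

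| | 491 h, CV 15% | 491 h, CV 30% | 832 h, CV 15% | 832 h, CV 30% |
|---|---|---|---|---|
| t½ relative SE, n = 10 | 0.294 | 0.535 | 0.463 | 0.887 |
| t½ relative SE, n = 15 | 0.240 | 0.437 | 0.378 | 0.724 |
| CL relative SE, n = 10 | 0.258 | 0.477 | 0.432 | 0.833 |
| CL relative SE, n = 15 | 0.210 | 0.389 | 0.353 | 0.680 |
| SE log AUC(0–inf) ratio, all parameters free | 0.333 | 0.616 | 0.558 | 1.075 |
| same, clearance only | 0.320 | 0.551 | 0.533 | 0.955 |
| same, bioavailability only | 0.111 | 0.125 | 0.117 | 0.130 |
| SE log AUC(0–24h) ratio, free | 0.125 | 0.144 | 0.125 | 0.144 |
| SE log AUC(0–168h) ratio, free | 0.113 | 0.128 | 0.118 | 0.132 |

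The free row follows from the CL rows: √(0.258² + 0.210²) = 0.333 and √(0.833² + 0.680²) = 1.075.

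As 95% CI factors, exp(1.96 × SE):
- AUC(0–inf), free: 1.9 to 8.2.
- AUC(0–inf), clearance only: 1.9 to 6.5.
- AUC(0–inf), bioavailability only: 1.2 to 1.3.
- AUC(0–24h) and AUC(0–168h): about 1.25 to 1.33.

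Under a pure bioavailability change, every AUC is multiplied by the same factor. AUC(0–inf) then has the same ratio as AUC(0–24h).

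**Step 4: what within-window exposure can show.** Doubling clearance halves AUC(0–inf). In the one-compartment model it multiplies AUC(0–168h) by 0.895 (491 h) or 0.935 (832 h), a fall of 10.5% or 6.5%, and AUC(0–24h) by 0.984 or 0.991. Both changes lie inside the CI factors above.

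**The case against.** **Population modelling is meant for sparse data, and the times are still to be optimised.** Both are true, but the calculation is already a population design at optimal times. The plan leaves exact times open; it does not leave the day 7 limit open. Allowing repeat pricks on later days lowers the clearance-only SE only to about 0.28–0.85.

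**Other trials may supply information on moxidectin.** This stands in part: results from the group's other trials may inform the model. But 8.3 specifies no prior, and a prior on a clearance level common to both arms does not inform the difference between them. Knowing ka and V exactly leaves the clearance-only SE unchanged. In the extreme case where all monotherapy parameters were known exactly, only arm A's variance would remain. The SE would then be multiplied by √(6/15) = 0.632, giving 0.20–0.60, or CI factors of about 1.5–3.3. That is better but still imprecise, and adult data may not carry over to adolescents.

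**The magnitudes rest on assumptions.** This stands. Neither the CVs nor the compartment structure is in the documents, and the factor 8.2 comes from the least favourable corner. The ratio in step 1 needs no such assumption.

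**Stronger readings that the documents do not support.**
- A reader might infer that the whole moxidectin interaction objective fails. It does not: three of the five listed parameters are estimable within seven days.
- A reader might infer that the SE < 25% target is missed. Section 8.3 does not say which parameters it covers, or whether per arm or pooled. In the mildest case t½ meets it with n = 15 (24%), and with both arms pooled (0.294 × √(10/25) = 19%). The fair criticism is that its scope is unstated.
- A reader might infer that sections 2 and 4.3.6 contradict each other on prior data. Limited healthy-adult data are still available data. What can be said is that the cited reference does not, by its title, cover moxidectin.

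**Conclusion.** The point holds for t½ and AUC(0–inf) of moxidectin in the comparison of arm A with arm E. The window covers 0.20–0.34 of the stated half-life, and 79–87% of AUC(0–inf) would be extrapolated under mono-exponential decline. Under the stated assumptions, a between-arm AUC(0–inf) comparison that allows clearance to differ is too imprecise to interpret, and the version that is precise is redundant with AUC(0–24h). Following 8.3 as written would base part of the interaction judgement on two parameters that the fixed window cannot support.

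Model-derived Cmax, tmax and AUC(0–24h) are not affected. Neither are the ivermectin parameters or the primary endpoint. Severity is minor: one drug, at most 25 participants, secondary objective g.

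**What to change.** In section 8.3, for moxidectin:
1. Judge interaction on the model-derived Cmax, tmax and AUC(0–24h) already planned, plus an added AUC(0–168h).
2. Report t½ and AUC(0–inf) as descriptive only, each with its relative SE, and give the extrapolated share of AUC(0–inf).
3. State before analysis which parameter or parameters may differ with co-administration (bioavailability, clearance or all). State also which parameters SE < 25% covers, and whether per arm or pooled.
4. Limit the moxidectin interaction conclusion to exposure up to day 7.

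**Cost.** Analysis wording only; no new samples. There are fewer moxidectin interaction parameters, and a clearance interaction stays largely unassessed, as it already is with this window. That is why item 4 is needed.

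**Separate minor point, all drugs.** Section 8.3 takes Cmax and tmax as observed values and gives two routes to t½ (Monolix and a log-linear regression). Section 4.3.6 says that "instead of describing the PK profile for each participant separately, samples are allocated to different time points and individuals within the same treatment", so sparse samples do not yield observed individual values. Taking Cmax, tmax and t½ from the fitted mixed-effects model would reconcile the two sections at no cost.
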